TABLE 2: Aim 1 - Demand-Side Access Data Collection

		Methodology	Measures	Variables
Quant	a	Individual Baseline Survey BL / End DCI: 1601, 1602	Systematic sampled individuals (Women: 75 / cluster) (Men: 30 / cluster) Sample size: n = 315	Demographics: # of people / roles in household, genders, # of eligible women, # of women seeking screening, health seeking decision making process / power, cost concern, facility proximity, health practices and opinions, knowledge and opinions of partners of eligible clients.
	b	Individual Interval Interview DCI: 1603, 1604	Systematic sampled individuals (Women: 45 / cluster) (Men: 30 / cluster of sample a)	Socio-demographics: Age, gender, marital type/status, education level Behavioral risk factors: Sexual debut, lifetime sexual partners, gravity, parity, age at first birth, number of children, smoking status, diet Clinical risk factors: History of STI, weight, long-term oral contraceptive use Health literacy / seeking: Cervical cancer screening history & knowledge, preventative care opinions, health service utilization
Qual	C	Women's Focus Groups DCI: 1605	Purposive-sampled groups (women, 30-44 or 45-59) of sample a	Demand-side access ref Instruments ⁴² Ability to perceive: Health literacy, Health beliefs, Trust and expectations Ability to seek: Personal and social values, culture, gender, autonomy Ability to reach: Living environments, Transport, Mobility, Social support Ability to pay: Income, Assets, Social capital, Health insurance Ability to engage: Empowerment, Information, Adherence, Caregiver support

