To achieve Aim 1, we will orient 3 CGs in each cluster. Through a participatory process involving CG leaders, health service leaders, midwives, and community members (women and men) we will develop, field test, and refine quantitative individual-level surveys that gather access barriers data corresponding to the variables listed in Table 2. We will conduct quantitative **a) Individual Baseline Surveys** with the same enrolled women (up to 25) and the same 10 men in each site per cluster. These data will be collected at baseline and at the end of the study period (after 3 years). We will also conduct **b) Individual Interval Interviews** with the same women (up to 25) and the same 10 men in each site per cluster. These data will be collected at baseline and every six months through the end of the study period (after 3 years). Therefore, these data will be collected six (6) times. These pre-tested, approved standard individual-level questionnaires (close ended) will be administered (face-to-face) by an RA of the same gender as the participant in the participants' preferred language (Malinke, Pulaar, or French). We will also conduct **c) Women's Focus Groups**. Through these FGs we will collect qualitative data, from women stratified by age, describing demand-side access barriers and facilitators (Table 2). The Research Assistant will moderate the 45 minute FGs in the preferred language (Malinke, Pulaar, or French) and two PCVs will observe and record written observations in real time. We will audio record the sessions (to be transcribed into both French and English). The Research Assistant and PCVs will review the audio record and confirm all notes. Below are described the recruitment and enrollment procedures for these data collection events.

Recruitment and Enrollment of Participants Followed within Households

We will utilize a random cluster sampling method to select ten (10) households in each of the three (3) sites per cluster. We will convenience sample one woman and one man in each of the households among those

who express a willingness to participate. We will ensure that the ten (10) chosen households fall within the households where the educational Care Group intervention takes place. Given that each Care Group will cover between 80 and 100 households, we are expecting to enroll participants from 10% of the households where the Care Group intervention occurs.

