Detailed household sampling: The range of eligible **households** will be defined by the immediate community surrounding the health facility in each of the three sites per cluster. Using a map of the community, we will divide the community geographically into five clusters. We will designate one household on the map as the starting location. We will randomly select a number between one and the number of households in that section of the community. The Research Assistant (RA) will begin counting at the starting location and will approach the household corresponding to the random number. Eligible households must have at least one screening eligible woman (age 30 to 59) and one man (age 30 to 59). The RA will ensure that the household is eligible. The RA will follow the designated procedures for recruiting men and women into the study. This includes reading the RESEARCH INFORMATION SHEET and reading the RECRUITMENT SCRIPT. The RA will begin by asking if there is one woman AND one man in the house who would like to participate. From among those that express willingness to participate, the RA will convenience sample participants by alternate recruiting of a younger woman (Age 30 to 44) and an older woman (age 45 to 59) from households. By doing this, half of the homes (5) will have younger women participants and half (5) will have older women participants. Not all women and men participants from a home need to be married to each other, but it is preferable if at least half of the participating households have married partners as participants. The RA will recruit men between the ages of 30 and 59, with no differentiation between the number of younger and older men participating. If BOTH a man AND a woman in the same household agree to participate, the RA will continue with enrollment by reading the INFORMED CONSENT and obtain a signature with the SHORT FORM. IF the RA is NOT ABLE to recruit BOTH a man and a woman in the same household, this household and any individuals in it will be unable to participate in the study. The RA will thank them for their time and continue to the NEXT HOME designated through a randomly selected number to recruit participants until two households with one woman and one man each are included in the study. The RA will read the INFORMED CONSENT to each of the chosen participants separately and privately. The RA will obtain participant written consent with the SHORT FORM and will then enroll each participant by entering their contact information in the PARTICIPANT REGISTER. The RA will inform them separately of the data collection schedule.

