
Recruitment and Enrollment of Participants Followed within Care Groups

We will utilize a random sampling method to select five (5) Care Group Volunteers in the Care Group of each the three (3) sites per cluster. We will seek to enroll, longitudinally follow, and collect data on three (3) younger woman (age 30 to 44) and two (2) older women (age 45 to 59) in each care group over the course of the study. Given that each Care Group has between 8 to 15 volunteers, we are expecting to enroll 1/3 to 1/2 of all Care Group Volunteers across all sites.

Detailed Care Group Volunteer sampling: While visiting a care group meeting, the RA will read the RESEARCH INFORMATION SHEET. The RA will then read the RECRUITMENT SCRIPT and ask the women if they are interested to participate. The RA will record the names of each younger woman (age 30 to 44) who is interested in participating on separate pieces of paper. The RA will fold each piece of paper separately and place into a container. The RA will blindly draw three names. The RA will then record the names of each older woman (age 45 to 59) who is interested in participating on separate pieces of paper. The RA will fold each piece of paper separately and place them into a container. The RA will blindly draw two names. The RA will

read the INFORMED CONSENT and SHORT FORM to each of the chosen participants separately and privately. The RA will obtain participant written consent with the SHORT FORM and will then enroll each participant by entering their contact information in the PARTICIPANT REGISTER. The RA will inform them separately of the data collection schedule.

Recruitment and Enrollment of Participants for Women's Focus Groups

We will conduct two focus groups every six (6) months. Five (5) care group members will be convenience selected from each care group AND two to three (2-3) household women participants will be convenience sampled to participate in a younger women's (age 30 to 49) and an older women's (age 45 to 59) focus group every six (6) months over the course of the study.

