Detailed Care Group Focus Group Sampling: At the beginning of a Care Group Meeting, the RA will explain that she will be conducting a short focus group. The RA will read the FOCUS GROUP RECRUITMENT SCRIPT and ask for interest to participate. The RA will invite all present members of the Care Group who express interest to participate in a focus group. The RA will read the INFORMED CONSENT and SHORT FORM to each of the chosen participants separately. The RA will obtain participant written consent with the SHORT FORM, separately and privately, and will invite them into the private focus group area and introduce them to the observers.

Aim 3: Evaluate the impact of the intervention on initial screening uptake and re-screening rates. (See Table 4)

TABLE 4: Aim 3 - Initial & Sustained Change Data Collection

Methodology			Measures	Variables
Quantitative	g Document Review DCI: 1612	No human participants. Review of aggregated health service records.	Initial Uptake/ Sustained utilization	
A. Number/% of women screened for the first time, age stratified 1
 
B. Number/% of women being re-screened, age stratified
 
C. Number/% of positive screened women referred/treated (aggregated data only)

	a Individual Interval Interview DCI: 1603, 1604	Systematic sampled individuals followed over time. Sample size: n = 0 new of sample a		

To achieve aim 3, we will follow cluster-wide trends through aggregated health service data⁶⁹ and participant-level impact through individual interviews. **Health service data** (# of initial and re-screenings stratified by age and number of referred women who completed treatment) will be reported by each cluster to the district center through the standard reporting structure. These de-identified data are reported to the regional level where they will be collected. Through the individual interviews described in aim 1 above (Table 2), we will collect impact data within our participant population in the form of first-time and re-screenings.

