Women. Criteria for inclusion include: 1) female Senegal citizen between the ages of 30 and 59, 2) Resident in Kedougou Region, 3) eligible to seek cervical cancer prevention services at a designated health structure in the Kedougou Region, Senegal, 4) willing to participate in survey or interview assessments; and 5) able to give informed consent.

Men. Criteria for inclusion include: 1) male Senegal citizen between the ages of 30 and 59, 2) Resident in Kedougou Region, 3) living in a household with at least one woman eligible to seek cervical cancer prevention services at a designated health structure in the Kedougou Region, Senegal, 4) willing to participate in survey or interview assessments; and 5) able to give informed consent.

Care Group Volunteer. Criteria for inclusion include: 1) Senegal citizen participating as a Care Group volunteer, 2) Resident in the Kedougou Region, Senegal, 3) willing to participate in survey or interview assessments, and 4) able to give informed consent.

Exclusion Criteria

Participants will be excluded if they are

- No additional exclusion criteria exist.

Excluded or Vulnerable Populations

Special considerations of the involvement of women and minorities and the justification of the exclusion of minors are detailed below.

The total planned enrollment / Inclusion of Women and Minorities

1. Planned distribution of participants by sex/gender, race, and ethnicity - The total planned enrollment is:
 - a. Aim 1: 15 women from Care Groups for each site (3) per cluster (3) = 135. Ten women from households for each site (3) per cluster (3) = 90. Ten men from households per site (3) per cluster (3) = 90. This equals a total of 315 individuals (225 women and 90 men). There are no new participants in the focus groups.
 - b. Aim 2: Individual interview (no new participants) + Focus Groups (no new participants) + Document Review (no human participants) = 0 new participants
 - c. Aim 3: Individual interview (no new participants) + Document Review (no human participants) = 0

Total participants = 315

Of these we estimate that there will be 225 women and 90 men. Based on general population numbers for the Kedougou Region in the country of Senegal, we anticipate that 100% of participants will be from African descent. All participants (women and men) will be African and have been included in the "Black" category.

2. Subject selection criteria and rationale for selection –

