5.0 Sources of Material, Protection Against Risks and Informed Consent

Sources of Material.

Sources of research material will include: 1) **Individual Baseline surveys** of adults (21 and above) in households with screening eligible women, 2) **Individual Interval Semi-structured Interviews**: semi-structured interviews with target age women eligible for screening and receiving cervical cancer prevention services or men living in a household with target age eligible women, 3) **Focus Groups** with women or Care Group Volunteers, and 4) **Document Review**: de-identified, aggregated health service or care group data,

Individual Baseline surveys

The baseline survey will gather information through adults (age 30 to 59) willing and able to provide the requested information. Once surveyed, individuals from the same households will be followed over time and re-surveyed at each data collection period. The pre-tested standard individual baseline surveys (close ended) will be administered (face-to-face) in the participants' preferred language (Malinke, Pulaar, or French). These will be administered by a Senegalese Research Assistant with assistance by PCV research assistants. This data collection will occur at baseline and at the end of the data collection period. Peace Corps Volunteers will assist the PI and Co-I's in ensuring the fidelity of this data collection.

Individual Interval Semi-structured Interviews

All screening-eligible women and all men aged 30 to 59 in all selected households will be interviewed. The pre-tested standard individual-level questionnaires (semi-structured) will be administered (face-to-face) in the participants' preferred language (Malinke, Pulaar, or French). These will be administered by a Senegalese Research Assistant with assistance by PCV research assistants. Aim 1 (access determinants, cervical cancer risk), Aim 2 (screening recommendation), and Aim 3 (screening uptake / utilization) data will be collected through this interview. All sites will be monitored for consistent and accurate collection of this data. The data collection instrument will be employed at baseline and every 6 months during the data collection period. Peace Corps Volunteers will assist the PI and Co-I's in ensuring the fidelity of this data collection.

Focus Groups

Aim 1 Focus Groups:

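### Section 5.0 has every eligible household member give the interval interview, while recruitment and planned enrolment provide for one woman and one man per household

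*Protocol*

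**What the plan says.** - **Section 5.0, Individual Interval Semi-structured Interviews:** "All screening-eligible women and all men aged 30 to 59 in all selected households will be interviewed". The same paragraph says this interview supplies Aim 1, Aim 2 (recommendation) and Aim 3 (uptake and utilization) data.
- **Section 3.0, household recruitment:** "We will convenience sample one woman and one man in each of the households among those" who are willing. The detailed sampling text repeats this: "the RA will convenience sample participants by alternate recruiting of a younger woman" in one household and an older one in the next. In each of five parts of the community, recruitment goes on "until two households with one woman and one man each are included in the study". Consent and entry in the participant register are described for the chosen persons only.
- **Section 4.0, planned enrollment:** "Ten women from households for each site (3) per cluster (3) = 90", the same number of men, and 135 Care Group women, for a total of 315.
- **Tables 2 to 4 (section 3.0), same instruments 1603 and 1604:** Table 2 has "Systematic sampled individuals (Women: 45 / cluster") and 30 men per cluster. Table 4 has "Systematic sampled individuals followed over time". Table 3 labels the respondents convenience and purposive. All three refer to sample a.
- **Section 3.0, Care Group Volunteer sampling:** interested women's names go into a container. "The RA will blindly draw three names" from the younger group and two from the older, so five per site. Section 4.0 counts 15 per site.

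**The concern.** The interval interview carries the participant-level outcomes for Aims 2 and 3, and the protocol gives two incompatible rules for who answers it.

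A field team following section 5.0 literally would interview people who are outside the planned enrolment, are not in the register and have not been through the described consent step. A team following section 3.0 would not. Three clusters followed for three years could apply different rules.

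The choice also affects the analysis. Section 6.0 plans a mixed-effects logistic model with household as a level. For the women-only screening outcome, one woman per household makes the household effect inseparable from the person effect among household respondents. With all eligible women interviewed, they are two distinct levels.

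A second, smaller issue is how the one woman and one man are chosen. The research assistant picks by convenience among willing members, although for volunteers the same staff already use a blind draw. The hypotheses in section 3.0 are stated as absolute levels (30% recommending, 35% initial uptake, 30% re-screening), and such levels depend on who is chosen.

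**Working it through.** **1. Reproduce the plan's total.** Section 4.0 has 15 Care Group women, 10 household women and 10 household men per site, with 3 sites in each of 3 clusters:
(15 + 10 + 10) × 3 × 3 = 135 + 90 + 90 = 315. It reproduces.

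**2. Link it to households.** Section 3.0 has five parts of each community with two households each: 5 × 2 = 10 households per site, and 10 × 3 × 3 = 90 households. Ninety women and 90 men from 90 households means exactly one of each per household.

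**3. Apply the section 5.0 rule.** Let *w* and *m* be the mean numbers of eligible women and men per selected household, and *V* the number of Care Group women. Then N = V + 90w + 90m. The protocol does not give *w* or *m*. It requires one or more of each, so 1 is the floor. The range 1 to 3 women and 1 to 2 men is an assumption.

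| w | m | 90(w + m) | N with V = 135 | N with V = 45 |
|---|---|---|---|---|
| 1 | 1 | 180 | 315 | 225 |
| 2 | 1 | 270 | 405 | 315 |
| 2 | 2 | 360 | 495 | 405 |
| 3 | 2 | 450 | 585 | 495 |

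The excess is 90(w − 1) + 90(m − 1), which runs from 0 to 90 × 2 + 90 × 1 = 270. It does not depend on *V*.

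**4. Why two values of V.** Section 4.0 gives 15 × 9 = 135 volunteers. The volunteer sampling text gives 5 × 9 = 45. For the interval interview, Table 2 has (45 + 30) × 3 = 225 people. Its 45 women per cluster are 15 per site, which fits 10 household women plus 5 volunteers. The running text of section 3.0 allows up to 25 women and 10 men per site, (25 + 10) × 9 = 315, which fits 10 plus 15. The base is therefore 225 or 315, depending on which passage governs.

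**5. Mix of women.** The share of household women is 90w / (90w + V).
- V = 135: 90/225 = 40% at w = 1; 180/315 = 57% at w = 2; 270/405 = 67% at w = 3.
- V = 45: 90/135 = 67% at w = 1; 180/225 = 80% at w = 2; 270/315 = 86% at w = 3.

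This matters because the volunteers are themselves the peer educators.

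**6. Selection within the household.** No figure in the protocol allows the effect of convenience choice to be sized.

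**The case against.** The strongest reply is that section 5.0 is loosely worded and that everything operational agrees on one woman and one man. Recruitment, consent, the register, follow-up of the same people and the count of 315 all point that way. That is a good reason to correct section 5.0 rather than the other sections. It does not remove the conflict, because the sentence defines respondents by eligibility within selected households, not by enrolment. The protocol also foresees households with several eligible women: Table 2 records their number.

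A reader might infer from the table labels that Tables 2, 3 and 4 describe different groups of people. The documents do not support that. Each ties the interview to sample a, and section 4.0 adds no new participants for Aims 2 and 3. The labels conflict, but the people are the same.

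A reader might also infer that convenience choice biases the estimated intervention effect. That goes too far. Section 5.0 takes consent at study initiation, the screening curriculum goes only to clusters that have crossed over, and section 6.0 compares the same participants before and after. Choosing a more accessible woman at enrolment mainly affects representativeness. Discretion is limited as well: households come from random numbers, the woman's age band alternates, and both a man and a woman must agree. The volunteer draw is likewise only among those interested. Cluster-wide uptake also comes from aggregated service records, which do not depend on who is interviewed.

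What remains is one real contradiction, one inconsistent label and a selection step that can be tightened cheaply.

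**Conclusion.** The point holds. The respondent rule in section 5.0 contradicts sections 3.0 and 4.0, and the sampling label for the same interview differs between Tables 2 and 4 on one side and Table 3 on the other.

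The size depends on household composition, which the protocol does not state. The excess is zero with one eligible woman and one eligible man in every household. It reaches 270 people at the top of the assumed range. A reader might take a large overshoot as certain, but the text does not establish that.

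The five-versus-15 volunteers per site sets the base for every total and every share of women, so it must be settled with the respondent rule. Convenience choice within the household is a weakness mainly for the absolute rates of 30%, 35% and 30%. Its effect cannot be quantified from the document.

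**What to change.** 1. **Section 5.0.** Replace the sentence with: *the enrolled woman and enrolled man in each selected household, and the enrolled Care Group volunteers, will be interviewed.* The volunteers must be named. Household women alone give 30 per cluster, not the 45 in Table 2.
2. **Section 3.0, household recruitment and detailed household sampling.** Replace convenience choice by the blind paper draw already described for volunteers: one draw among willing eligible women of the required age band and one among willing eligible men.
3. **Tables 2, 3 and 4.** Give the interval interview one sampling description that covers both household participants and volunteers.
4. **Volunteer numbers.** State one number per site, and carry it through the volunteer sampling text, Table 2, the running text on the interval interview and section 4.0.

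Items 1, 3 and 4 are wording, though item 4 needs a decision. Item 2 should take about a minute per household, or roughly 90 minutes over 90 households, and adds no participants.

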Through aim 2 we will develop a curriculum intended for a multi-level audience to motivate women to seek cervical cancer screening services. The curriculum (informed by aim 1) will be adapted from the WHO “Comprehensive Guide to Cervical Cancer Control: A guide to essential practice. 2nd edition⁶⁸” materials by key individuals (including health leaders, midwives, matrones, CHWs, screening eligible women, men, religious leaders, traditional healer, and PCVs). The curriculum will be comprised of educational materials in French and local language (Malinke and Pulaar). CGs will deliver the curriculum content. We will orient the CG leaders on the curriculum and provide comprehensive guidance on the research protocol throughout the study period. Each CG will transmit general health education from the initiation of the study. Only CGs within clusters that have crossed over into the intervention arm will be provided with the cervical cancer screening curriculum. We will collect quantitative program reach and recommendation data and qualitative process and program satisfaction data at each time period. The Individual Interval Interview data contributing to this aim will be collected through the same data collection event described for AIM 1. All data contributing to this AIM will be used to adapt the intervention over time. We will collect quantitative data through **document review** of CG records (number of individuals, households, and communities directly receiving the intervention) or through individual survey or interview (Table 3). We will also conduct one **FG** per site (3 per cluster) per data collection period (at baseline and every six months) through the end of the study (3 years) for aim 2 to gather qualitative data that describe the peer educator (volunteers from each CG) opinion of the peer education program (Table 3). The RA will moderate the 45 minute focus groups in the preferred language (French, Malinke or Pulaar) and two PCVs will observe and record written observations in real time. We will audio record the sessions (and transcribe into French and English). The moderating CG district coordinator and PCVs will review the audio record and confirm all notes.

Recruitment and Enrollment of Participants for Care Group Focus Groups

We will conduct one focus group every six (6) months in each site. All present Care Group members will be invited to participate.

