4.0 Recruitment, Eligibility and Enrollment

Recruitment

The PI ([name]) and Senegalese Co-I's ([name] and [name]) will train all research assistants, matrones and community health committee leaders at a designated intervention cluster in the Kedougou Region, Senegal. Through our prior work, we have worked directly with each of these individuals. The research assistants, with oversight by the Peace Corps Volunteer research assistants and the Co-I's and PI, will recruit individuals, households, and focus group participants (as described above in section one). The lead Peace Corps Volunteer who is in charge of recruitment, informed consent, participant tracking, and data collection is a UIC MPH trainee (in Senegal as a Peace Corps Volunteer). She is listed as a key personnel on the protocol. These individuals will explain the purpose and activities of the study, and select those who: 1) are confirmed to meet the criteria; and 2) are able to give informed consent. See Inclusion Criteria above.

After the participants give consent, they will participate in the surveys, interviews or focus groups during each data collection period. Drs. [name] and [name] and a Peace Corps Volunteer (MPH level) will oversee preparation of the RA's for the moderation of interviews and focus groups. See detailed description of sources of material.

Human Subjects Involvement and Characteristics.

Throughout this discussion of Human Subjects, "subjects" are referred to as "participants." Inclusion criteria and procedures for each aim of the study are described below.

Determination of Subject Eligibility

The Principal Investigator, Co-Investigators, and onsite Research Personnel will oversee subject eligibility. Eligibility will be determined at the time of recruitment and consent. The Senegalese Co-Investigators ([name], [name]), in collaboration with the U.S. Principal Investigator ([name]) and Project Coordinator, will oversee recruitment. No compensation will be awarded for direct involvement in focus groups or for completion of surveys. However, refreshments may be provided at the time of the focus group. An eligibility checklist in the form of a recruitment script is attached.

Inclusion Criteria

The inclusion criteria are as follows:

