There will be two **FGs** (women ages 30 to 44 and ages 45 to 59) per cluster every 6 months throughout the study period. Through FGs we will collect qualitative data, from women stratified by age, which describe demand-side access barriers and facilitators (Table 2). The Senegalese research assistant will moderate the 45 minute FGs in the preferred language (Malinke, Pulaar, or French) and two PCVs will observe and record written observations in real time. We will audio record the sessions (to be transcribed into both French and English). The Research Assistant and PCVs will review the audio record and confirm all notes. The women enrolled as individuals will make of the focus groups. There will be no new women enrolled for this data collection activity.

Aim 2 Focus Groups:

We will conduct two **FGs** per cluster per data collection period for aim 2. Through the FGs we will gather qualitative data that describe the peer educator (matrone and the volunteers from each CG) opinion of the peer education program (Table 3). The CG district coordinators will moderate the 45 minute focus groups in the preferred language (French, Malinke or Pulaar) and two PCVs will observe and record written observations in real time. We will audio record the sessions (and transcribe into French and English). The moderating CG district coordinator and PCVs will review the audio record and confirm all notes.

Participants will include 15 CG volunteers that comprise the FGs in each cluster (no new participants). The women participants are not newly enrolled and are the same as described in the FG activity in Aim 1.

This data collection will occur at baseline and every 6 months during the data collection period. Peace Corps Volunteers will assist the PI and Co-I's in ensuring the fidelity of this data collection.

Document Review – Uptake Data

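### The protocol names two different moderators for the Aim 2 Care Group focus groups, one of them a programme coordinator, and also disagrees on the number of groups and who attends

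*Protocol*

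**What the plan says.** **Moderator.** The Aim 2 text in Section 3.0 says "The RA will moderate the 45 minute focus groups in the preferred language (French, Malinke or Pulaar"). The last sentence on these groups in the same paragraph reads "The moderating CG district coordinator and PCVs will review the audio record and confirm all notes". In Section 5.0, under Aim 2 Focus Groups, the statement is "The CG district coordinators will moderate the 45 minute focus groups in the preferred language", and the coordinator is again given review of the recording together with the PCVs.

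Two other places support the RA. The detailed Care Group focus group sampling text in Section 3.0 has it that "the RA will explain that she will be conducting a short focus group". Section 4.0, under Recruitment, says that senior team members "will oversee preparation of the RA's for the moderation of interviews and focus groups".

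**Number of groups.** Section 3.0 plans one group "per site (3 per cluster) per data collection period (at baseline and every six months"), and the recruitment paragraph that follows repeats it: "We will conduct one focus group every six (6) months in each site". Section 5.0 plans two groups "per cluster per data collection period for aim 2".

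**Participants.** Section 3.0 invites every Care Group member present at the meeting. Section 5.0 counts 15 Care Group volunteers per cluster and describes them as the same women as in the Aim 1 focus groups.

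**The concern.** These groups ask peer educators what they think of the peer education programme. Table 3 lists them as the source for process and programme satisfaction, and the Aim 2 text in Section 3.0 says that the data for this aim will be used to adapt the intervention as it proceeds.

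The Peer Education text in Section 3.0 places the district-level Care Group coordinator inside the programme, with a regional manager overseeing it. If the coordinator moderates and then reviews the tape, volunteers give their opinion of the programme to someone who belongs to it. The protocol's own risk section recognises that Care Group volunteers may worry about colleagues learning what they said. Reluctance to criticise is a plausible result, and the adaptations would then rest on feedback that is too favourable.

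There is also a practical problem. A field team cannot follow both versions. If districts settle on different ones, the type of moderator will differ by district, and the clusters are the districts. Differences in feedback between clusters could then not be separated from differences in who asked the questions.

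**Working it through.** No power or error-rate calculation applies. The check sets the texts side by side and counts groups.

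| Item | Section 3.0 | Section 5.0 | Elsewhere |
|---|---|---|---|
| Moderator | RA, then the coordinator in the same paragraph | Coordinator | RA (sampling text in 3.0; training in 4.0) |
| Review of the recording | Coordinator and PCVs | Coordinator and PCVs | – |
| Groups per cluster per round | 3 (one per site) | 2 | 1 per site (recruitment paragraph in 3.0) |
| Participants | All members present | 15 volunteers per cluster | – |

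**Reading the moderator row.** The conflict lies between sections and also within one paragraph of Section 3.0. Three statements point to the RA: the first in the Aim 2 paragraph, the sampling text and the training text. The coordinator is called the moderator at the end of the Aim 2 paragraph and in Section 5.0. No passage describes preparing coordinators to moderate.

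**Groups per round.** Inputs: 3 clusters (Section 6.0, Power calculations) and 3 sites per cluster.
- Section 3.0: 1 per site × 3 sites = 3 per cluster, which matches the figure given there; 3 × 3 clusters = 9 per round.
- Section 5.0: 2 × 3 clusters = 6 per round.
- Difference: 9 − 6 = 3 groups per round, and 3 / 9 = one third.

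**Study totals (assumption on rounds).** The protocol gives no total number of rounds for these groups.
- Six rounds, the count that Section 3.0 gives for the interval interviews: 9 × 6 = 54 against 6 × 6 = 36.
- Seven rounds, meaning baseline plus every six months up to 36 months: 9 × 7 = 63 against 6 × 7 = 42.

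**Participants per cluster per round.**
- Section 3.0, with 8 to 15 volunteers per Care Group (Care Group recruitment text) and full attendance: 3 × 8 = 24 to 3 × 15 = 45. With the 10 to 15 per group in the Peer Education text: 3 × 10 = 30 to 45.
- Section 5.0: 15. This equals 5 × 3, the five sampled volunteers from each of three Care Groups.

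**The case against.** The strongest reply is that this is leftover wording. Most of the text points to the RA, and a sensible team would use the RA. That is likely, but the protocol does not say so, and Section 5.0 is an explicit statement to the contrary.

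A second reply is that the design is participatory by intent. The Peer Education text has Care Group administrators, leaders and volunteers, alongside the PCVs, collecting data. Some programme involvement is therefore deliberate, and this point does not ask for the coordinator to be barred from the room. It does not explain why one session has two named moderators.

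A third is that safeguards exist. Two PCVs observe and take notes, sessions are recorded and transcribed, and coding is done by the university teams. These protect the record of what was said. They do less for what volunteers are willing to say, and one PCV per district works with that same coordinator.

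Some stronger readings are tempting and should be resisted:
- A reader might infer that two groups per cluster leave one of three sites unevaluated. Section 5.0 never ties a group to a site. Its 15 volunteers fit five from each of three Care Groups, and the Aim 1 groups to which it refers number two per cluster and are split by age. Two cross-site groups would lose no site.
- A reader might infer that the coordinator manages or runs the Care Groups. The Peer Education text gives training and supervision to the lead matrone and oversight to the regional manager. It says only that a coordinator exists at district level and works with a PCV.
- A reader might infer that the Aim 2 result as a whole is biased. The Aim 2 hypothesis (75% reach, better knowledge, 30% recommending) rests on document review and individual interviews, which these groups do not touch.

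**Conclusion.** The contradiction is real and unresolved on three items: moderator (with review of the recording), number of groups, and participants. The firm figures are 9 against 6 groups per round, and a possible 24 to 45 participants per cluster per round, if attendance is full, against 15. The totals of 54 against 36, or 63 against 42, depend on an assumed six or seven rounds.

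The consequence is limited to the qualitative process and satisfaction strand of Aim 2 and to the adaptations drawn from it. That coordinator moderation would soften criticism is a reasonable inference from the coordinator's role. The protocol does not state it, and its size cannot be estimated from the document. The point is minor, but it is more than clerical, because the choice decides who elicits and checks the volunteers' opinions.

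**What to change.** 1. In Section 5.0, Aim 2 Focus Groups, replace the district coordinator with the RA as moderator and, with the PCVs, as reviewer of the recording.
2. Make the same replacement in the closing sentence on these groups in the Aim 2 text of Section 3.0.
3. State in both sections one group per site (three per cluster) per round, with all Care Group members present invited, as the recruitment and sampling text in Section 3.0 already has it. Amend the sentence on 15 volunteers per cluster in Section 5.0 to match.
4. State the number of rounds for these groups.

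The cost is wording. Under the Section 3.0 text the RA already attends these meetings, obtains consent and conducts the group, and Section 4.0 already provides for the RA's preparation as moderator. If field work was planned on the Section 5.0 count, the change adds 3 sessions of 45 minutes per round across the region (3 × 45 = 135 minutes), plus their transcription. Inviting all members present stays within the Care Group enrolment planned in Section 4.0 (15 per site × 9 sites = 135 women).
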